6.2. Specification of Baseline Values

A participant's baseline MMDs/MHDs will be the total number of headache/migraine days recorded during the 28-day run-in period. Baseline MMDs is a subset of baseline MHDs.

For endpoints not mentioned above, a baseline value is the latest value measured during the baseline visit or prior to baseline visit.

6.3. Handling of Missing Data

Participants should complete the eDiary on a daily basis during the 28 days of the run-in period and the 12 weeks of treatment. In the eDiary, the participants report whether they experienced a headache during that day including the start and end time, symptoms, and usage of acute medications. The eDiary allows for retrospective reporting of headaches up to 48 hours.

7. STUDY POPULATION

7.1. Participant Disposition

This analysis will be done on the consented analysis set.

The number of participants who were screened, completed the run-in period, and were randomized into the study will be presented. The number of participants who started treatment, and number of participants who discontinue the study will be presented by reason for discontinuation. The number of participants in the consented, enrolled, ITT, mITT, PP, and safety analysis sets will be presented.

7.2. Demographics and Baseline Characteristics

In order to assess the comparability of the two arms at baseline, demographic and baseline characteristics data will be summarized by treatment group.

A summary table will be generated and will include sex, age (continuous and by age category), ethnicity, race, geographical region, income level, level of education, baseline MMDs (using the observed data), baseline MHDs (using the observed data), Low and High frequency episodic migraine classification at baseline, participant's current prescription migraine medications at baseline (acute only; preventive L1 with or without acute; preventive L2 with or without acute medications; other), baseline MSQ, baseline PHQ-8, baseline GAD-7 and baseline MIDAS.

Participants will be assigned to a race category according to their response. Participants who responded to the question about race with more than one race category will be assigned to the "Multiple" category.

7.3. Medical History and Medications

The medical history and medication analysis will be performed using the ITT analysis set.

Medical history will be summarized and presented by treatment group.

The proportion of participants who received previous therapy will be summarized by WHOdrug preferred term and presented by treatment group. A separate summary will be presented for migraine medications taken prior to the study.

The proportion of patients who report concomitant medications during study treatment will be summarized by WHOdrug preferred term and presented by treatment group regardless of whether the medication was taken prior to baseline.

Previous therapy is defined as medication with end date earlier than the baseline date (study app activation).

Concomitant medication is defined as medication with an end date on or later than the baseline date (study app activation) or missing end date.

The proportion of participants who use acute migraine medication and preventive migraine medication will be summarized, separately, by WHOdrug preferred term and presented by treatment group.

7.4. Protocol Deviation

The protocol deviations will be documented in a deviation tracker and classified into major and minor deviations.

The number of protocol deviations and the proportion of subjects (%) with at least one deviation will be shown for the ITT set. The summary will include the deviation category (Informed Consent, Inclusion/Exclusion, etc.) and deviation severity (minor/major) and will be presented by treatment arm.

7.6. Exposure

Exposure to study intervention, in days, will be calculated for each participant as number of days from first day of treatment until last day of treatment + 1. First day of treatment is defined as the first date with adherence to task and last day of treatment is defined as the last date of adherent to task.

Exposure will be summarized using descriptive statistics by treatment group.

8. EFFECTIVENESS ANALYSIS

Unless otherwise specified, all effectiveness analyses will be conducted on the ITT set. For several endpoints, the analyses will be repeated for other analysis sets, as described for the relevant endpoints in the sections below.

For all endpoints, descriptive statistics will be presented by treatment group and by visit/weeks where applicable. Actual value and change from baseline (where applicable) will be presented.

Several endpoints are based on MMDs and MHDs. For details regarding qualification of headache as migraine please refer to Appendix A - Data Specifications in this document, Section 6.4. For details regarding derivation of MMDs please refer to Section 7 in this appendix. For details regarding derivation of MHD, please refer to Section 8 of this appendix.

8.1. Primary Effectiveness Endpoint and Analysis

8.1.1. Primary Effectiveness Endpoint

The primary endpoint is change in MMDs from baseline (28-day run-in period) to Week 12 (previous 28 days, Week 9 through Week 12).

Baseline MMDs will be calculated as the number of MMDs in the 28-day run-in period.

The Week 12 MMDs will be calculated as the number of MMDs in the 28 days during Weeks 9-12.

The change from baseline to Week 12 will be calculated as (Week 12 MMDs – baseline MMDs).

In case of missing eDiary days, the MMDs will be imputed as described in Section 6.3, resulting in 100 complete data sets.

8.1.2. Primary Hypotheses

The null hypothesis that will be examined for the primary effectiveness endpoint is that there is no difference in effectiveness between the CT-132 treatment arm and the control in regard to the change from baseline (28-day run-in period) to Week 12 (previous 28 days, Week 9 through Week 12) in MMDs:

H₀:
$$\mu$$
_CT132 = μ _DC
H₁: μ _CT132 \neq μ _DC

Where μ _CT132 is the mean change from baseline (28-day run-in period) to Week 12 (previous 28 days, Week 9 through Week 12) in MMDs for the CT-132 treatment arm and μ _DC is the mean change from baseline (28-day run-in period) to Week 12 (previous 28 days, week 9 through Week 12) in MMDs for the digital control arm.

The success criterion for the study is rejection of the null hypothesis as defined above with a two-sided 0.05 alpha level.

8.1.3. Primary Effectiveness Analysis

An Analysis of Covariance (ANCOVA) model will be used to analyze the primary endpoint. The dependent variable is the change from baseline to Week 12 in MMDs for each participant.

The model will adjust for the following covariates: treatment arm, baseline MMDs, and baseline use of concomitant medications for prevention of migraine. The analysis will be conducted on the ITT analysis set.

Each of the 100 complete datasets will be analyzed using this model. Rubin's rule will be used to combine the results from each of the 100 analyses, resulting in LS mean for the treatments difference and *p*-value associated with the treatment effect. The 95% confidence interval (CI) for the treatment difference will also be constructed. This is considered as the primary analysis for the study, and the study will be considered successful if the p-value is less than 0.05.

LS means for the change from baseline, within each arm as well as the SE, 95% CI and *p-value* for the null hypothesis of no change from baseline versus the two-sided alternative will be presented.

8.2. Supportive Analyses

8.2.1. Non-parametric Analysis

The primary analysis described in Section 8.1.3 assumes that the primary endpoint is normally distributed. In order to evaluate the robustness for this assumption, Wilcoxon rank-sum test will be conducted on the primary endpoint, for each of the 100 complete datasets. The results from the 100 analyses will be pooled by extracting the variability for each dataset and then using Rubin's rule.

8.2.2. Responder analysis for different thresholds

In order to describe the magnitude of change within each treatment group in a different way than mean change in MMD, a summary table with descriptive statistics will show the proportion of participants, within each arm, with change from baseline (CFB) in MMDs for different response thresholds, ranging from CFB=0 to CFB=-7.

8.3. Sensitivity Analyses

8.3.1. Tipping Points Analysis

To evaluate the robustness of the results of the primary analysis to the MAR assumption, a tipping point analysis will be performed as follows:

This analysis consists of a series of analyses, using the same model as for the primary analysis, but using Missing Not at Random (MNAR) imputations instead of MAR, as defined in Section 6.3,

Under MNAR, assuming smaller and smaller treatment effects until the first time the statistical significance is lost, and study conclusions revert.

This point is considered the "tipping point". The treatment effect is then evaluated for its plausibility. If it is not considered plausible then the robustness of the results is supported.

8.3.2. No imputation Analysis

The primary analyses will be repeated using the observed data only, without imputations.

8.3.3. mITT analysis set Analysis

The primary analysis will be repeated using the mITT analysis set, using MI as detailed in Section 8.1.3.

8.3.4. Per Protocol Analysis

The primary analysis will be repeated using the Per Protocol analysis set, using MI as detailed in Section 8.1.3.

8.5. Secondary Effectiveness Endpoint and Analysis

Unless otherwise specified, all secondary analyses will be performed on the ITT analysis set.

8.5.1. Proportion of participants who have at least a 50% reduction from baseline (28-day run-in period) in the number of MMDs to Week 12 (previous 28 days, Week 9 through Week 12)

This endpoint will be performed on the mITT analysis set, in addition to the ITT analysis set.

Define R = ((Week 12 (previous 28 days, Week 9 through Week 12) MMDs - Baseline (28-day run-in period) MMDs) / Baseline (28-day run-in period) MMD) *100

For each of the 100 complete datasets, each participant will be indicated as "responder" at week 12 if the reduction is 50% or more (i.e., $R \le 50\%$), and "non-responder" otherwise.

The proportion of patients who have at least a 50% reduction in MMDs will be compared between the two treatment groups using the normal approximation for difference between two proportions, for each of the complete data sets. The results will be combined using Rubin's rule.

8.5.2. Change from baseline (28-day run-in period) in number of MMDs recorded over the previous 28 days at Week 4

The endpoint will be analyzed, using the 100 complete datasets, in the same manner as the primary endpoint.

The week 4 MMDs will be calculated as the number of MMDs in Days 1-28.

8.5.3. Change from baseline (28-day run-in period) in number of MMDs recorded over the previous 28 days at Week 8

The endpoint will be analyzed, using the 100 complete datasets, in the same manner as the primary endpoint.

The week 8 MMDs will be calculated as number of MMDs in the 28 days during Weeks 5-8 (Days 29-56).

8.5.4. Change from baseline (28-day run-in period) in the mean number of MMDs over 12 weeks

This endpoint will be performed on the mITT analysis set, in addition to the ITT analysis set.

The monthly number of MMDs over 12 weeks will be calculated as the average of MMDs over Weeks 1-4, MMDs at Weeks 5-8, and MMDs at Weeks 9-12, to get the average monthly MMDs. The average monthly MMDs will be used in order for the MMDs over 12 weeks to be comparable with the baseline (end of run-in period) MMDs.

The change from baseline will be calculated as the monthly number of MMDs over 12 weeks minus the baseline MMDs.

The endpoint will be analyzed, using the 100 complete datasets, in the same manner as the primary endpoint.

8.5.5. Change in the number of headaches with at least moderate severity from baseline (28-day run-in period) to Week 12 (previous 28 days, Week 9 through Week 12)

This endpoint will be performed on the mITT analysis set, in addition to the ITT analysis set.

Each recorded headache's severity will be scored in the following manner:

- None = 0
- Mild = 1
- Moderate = 2
- Severe = 3

Headaches that started at one period and ended in the following period will be assigned to the period in which the headache started.

The change from run-in will be calculated as (Weeks 9-12 number of headaches with at least moderate severity – run-in number of headaches with at least moderate severity).

An ANCOVA model will be used to analyze this endpoint. The dependent variable is the change in number of headaches with at least moderate severity from run-in period to Week 9-12 for each participant.

The model will adjust for the following covariates: treatment arm and number of headaches with at least moderate severity at run-in period

This analysis will use observed data only.

8.5.6. Change from baseline in the Migraine-Specific Quality-of-Life Questionnaire v2.1 (MSQ) total score at Week 12

The MSQ is a 14-item questionnaire that is completed at baseline, Week 4, Week 8, and Week 12. Each item consists of 6 possible responses, scored 1 to 6. Higher scores represent more severe migraines.

For the purpose of calculating the MSQ total score, the responses to the 14 items will be reverescoded (scores 1,2,3,4,5,6 will be converted to 6,5,4,3,2,1 respectively)

For each visit, the MSQ score (after reverse-coding) will be calculated as:

Total score = ([sum of the 14 reversed item scores - 14] / 70) * 100

In case of missing items, the MSQ score for the visit will be considered missing.

An ANCOVA model will be used to analyze this endpoint. The dependent variable is the change from baseline in MSQ to week 12 for each participant.

The model will adjust for the following covariates: treatment arm and baseline MSQ.

This analysis will use observed data only.

8.5.7. Change from baseline in the Migraine-Specific Quality-of-Life Questionnaire v2.1 (MSQ) total score at Week 8

This endpoint will be analyzed in the same manner as described in Section 8.5.6, using the Week 8 assessment.

8.5.8. Change from baseline in the Migraine-Specific Quality-of-Life Questionnaire v2.1 (MSQ) total score at Week 4

This endpoint will be analyzed in the same manner as described in Section 8.5.6, using the Week 4 assessment.

8.5.9. Change from baseline (28-day run-in period) in the Migraine Disability Assessment (MIDAS) to Week 12

The MIDAS questionnaire assesses the impact the migraine has on the participant's life. It consists of 5 questions regarding the number of days impacted. In addition, there are two questions for physician use. The endpoint will use only the first 5 questions. The MIDAS score for a visit is the sum of responses of the first 5 questions. In case of missing items, the MIDAS score for the visit will be considered missing.

This endpoint will be analyzed using Wilcoxon rank-sum test.

This analysis will use observed data only.

8.5.10. Change from baseline (28-day run-in) period to Week 12 (previous 28 days, Week 9 through Week 12) in the number of migraines with use of an acute medication

This endpoint will be performed on the mITT analysis set, in addition to the ITT analysis set.

The number of migraines with use of an acute medication will be counted for the run-in period and for post randomization period.

The change from baseline will be calculated as number of migraines in weeks 9-12 minus number of migraines in the run-in period with use of an acute medication.

Migraines that started at one period and ended in the following period will be assigned to the period in which the migraine started.

An Analysis of Covariance (ANCOVA) model will be used to analyse this endpoint. The dependent variable is the change from baseline to Week 12 in the number of migraines with use of an acute medication each participant.

The model will adjust for the following covariates: treatment arm, baseline number of migraines with use of an acute medication. The analysis will use only observed data.

8.5.11. Change in the number of MHDs from baseline (28-day run-in) to Week 12 (previous 28 days, week 9 through Week 12)

This endpoint will be calculated and analyzed as described in Section 8.1.3, using MHDs instead of MMDs.

[figure not shown]
This endpoint will be performed on the mITT analysis set, in addition to the ITT analysis set.

[figure not shown]

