#### **9.4.4.2. Subgroups**

### 9.4.5. Secondary Endpoints

Analysis of secondary endpoints will include the ITT set.

- Proportion of participants that have at least 50% reduction from baseline (28-day run-in period) in the number of MMDs to Week 12 (previous 28 days, Week 9 through Week 12). The proportion of patients who have at least a 50% reduction in MMDs will be compared between the two treatment groups using the normal approximation for difference between two proportions, for each of the complete data sets. The results will be combined using Rubin's rule.
- Change from baseline (28-day run-in period) in the number of MMDs recorded over the previous 28 days at Week 4 and at Week 8 will be analyzed in the same manner as the primary endpoint.
- Change from baseline (28-day run-in period) in the mean number of MMDs over 12 weeks. The endpoint will be analyzed in the same manner as the primary endpoint.
- Change in the number of headaches with at least moderate severity from baseline (28-day run-in period) to Week 12 (previous 28 days, Week 9 through Week 12). An ANCOVA model will be used to analyze this endpoint.
- Change from baseline (28-day run-in period) in the Migraine-Specific Quality-of-Life Questionnaire v2.1 (MSQ) total score over the previous 28 days at Week 4, Week 8, and Week 12. An ANCOVA model will be used to analyze this endpoint.
- Change from baseline in the Migraine Disability Assessment (MIDAS) to Week 12. This endpoint will be analyzed using Wilcoxon rank-sum test.

- Change from baseline (28-day run-in) to Week 12 (previous 28 days, Week 9 through Week 12) in the number of migraines with use of an acute medication. An ANCOVA model will be used to analyze this endpoint.
- Change in the number of MHDs from baseline (28-day run-in period) to Week 12 (previous 28 days, Week 9 through Week 12). The endpoint will be analyzed in the same manner as the primary endpoint, using MHDs instead of MMDs.

The SAP will elaborate on the analysis of other endpoints, covariates and handling of missing data.

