3.2. Secondary Effectiveness Endpoints

- Proportion of participants who have at least a 50% reduction from baseline (28-day run-in period) in the number of MMDs to Week 12 (previous 28 days, Week 9 through Week 12).
- Change from baseline (28-day run-in period) in the number of MMDs recorded over the previous 28 days at Week 4 and at Week 8.
- Change from baseline (28-day run-in period) in the mean number of MMDs over 12 weeks.
- Change in the number of headaches with at least moderate severity from baseline (28-day runin period) to Week 12 (previous 28 days, Week 9 through Week 12).
- Change from baseline (28-day run-in period) in the Migraine-Specific Quality-of-Life Questionnaire v2.1 (MSQ) total score over the previous 28 days at Week 4, Week 8, and Week 12.
- Change from baseline (28-day run-in period) in the Migraine Disability Assessment (MIDAS) to Week 12 (previous 28 days, Week 9 through Week 12).
- Change from baseline (28-day run-in period) to Week 12 (previous 28 days, Week 9 through Week 12) in the number of migraines with use of an acute medication.
- Change in the number of MHDs from baseline (28-day run-in period) to Week 12 (previous 28 days, Week 9 through Week 12).

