8.7. Exploratory Endpoints

All exploratory analyses will be conducted on the ITT analysis set.

8.7.13. Proportion of participants who have at least a 50% reduction from baseline (28-day run-in period) in the number of MHDs at Week 12 (previous 28 days, Week 9 through Week 12)

This endpoint will be calculated and analyzed as described in Section 8.5.1, using MHDs instead of MMDs.

8.7.14. Change from baseline (28-day run-in period) in the mean number of MHDs over 12 weeks.

This endpoint will be calculated and analyzed as described in Section 8.5.4, using MHDs instead of MMDs.

8.7.15. Change from baseline (28-day run-in period) in the number of MHDs recorded over the previous 28 days at Week 4

This endpoint will be calculated and analyzed as described in Section 8.5.2, using MHDs instead of MMDs.

8.7.16. Change from baseline (28-day run-in) in the number of MHDs recorded over the previous 28 days at Week 8

This endpoint will be calculated and analyzed as described in Section 8.5.3, using MHDs instead of MMDs.

8.8. Patient Global Impression of Change (PGI-C) score at Week 12

The Patient Global Impression of Change (PGI-C) is a self-reported, 7-point scale depicting a patient's rating of overall improvement.

The PGI-C will be measured at Week 12.

T-test will be used to analyze this endpoint.

8.8.1. Shift from High Frequency Episodic Migraine (HFEM) at baseline (28-day runin period) to Very Low Frequency Episodic Migraine (VLFEM) or Low Frequency Episodic Migraine (LFEM) at Week 12 (previous 28 days, Week 9 through Week 12)

During the 28-day run-in period each participant will be classified as having High Frequency Episodic Migraine (HFEM; 8-14 MMDs) or Low Frequency Episodic Migraine (LFEM; 4-7 MMDs).

During weeks 9-12, participants will be classified as HFEM, LFEM or Very Low Frequency Episodic Migraine (VLFEM; < 4 MMDs). Note that per inclusion criteria at baseline there are no VLFEM participants.

A shift table will be presented including the number and percentage of participants shifting from each category at run-in period to each category at Weeks 9-12, by treatment group.

This analysis will include only subjects with at least 10 days of reporting during Week 9-12, and number of migraines will be prorated as described in Section 6.3. Patients with less than 10 days of reports will be considered missing in this analysis.

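### SAP 8.5.1: the responder cut-off reads R ≤ 50%, but with R defined as signed percent change a reduction of at least 50% is R ≤ -50%

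*SAP*

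**What the plan says.** SAP 8.5.1 defines R with Week 12 MMDs first in the numerator, followed by "MMDs - Baseline (28-day run-in period) MMDs) / Baseline (28-day run-in period) MMD) *100". That is a percent change, negative when MMDs fall. In each of the 100 imputed datasets a participant is then a responder "if the reduction is 50% or more (i.e., $R \le 50\%$), and" a non-responder otherwise.

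The endpoint itself is stated consistently. SAP 3.2 lists it as "Proportion of participants who have at least a 50% reduction from baseline (28-day run-in period) in the number of MMDs to Week 12". Protocol 9.4.5 says: "The proportion of patients who have at least a 50% reduction in MMDs will be compared between the two treatment groups".

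The sign convention is also consistent elsewhere in the SAP. In 8.1.1, "The change from baseline to Week 12 will be calculated as" Week 12 minus baseline, and the response thresholds in 8.2.2 run from 0 down to -7.

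For the exploratory responder endpoint on monthly headache days (MHDs), SAP 8.7.13 states: "This endpoint will be calculated and analyzed as described in Section 8.5.1, using MHDs instead of MMDs".

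**The concern.** The inequality is offered as a restatement of the words beside it, yet it describes a different set of participants. It is the only form of the rule in the available text that can be programmed directly, and it governs the first-listed secondary endpoint in both the ITT and mITT sets. If a programmer codes the symbol and not the words, people with no change, and people up to 50% worse, are counted as responders. Both arms' proportions would be inflated and the comparison between them distorted.

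The protocol's correct wording is not a formal safeguard, because SAP section 1 gives the SAP precedence where the two disagree. Here the conflict lies inside the SAP, so it has to be resolved there.

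**Working it through.** **Inputs.** R and the criterion come from SAP 8.5.1. Eligible baseline MMDs are 4 to 14 (Protocol 5.1, inclusion criterion 5). Each period has 28 days, so Week 12 counts run from 0 to 28. The frequency bands come from SAP 8.8.1.

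**Step 1: can the stated cut-off be reproduced?** Let B be baseline and W the Week 12 count, with R = 100 × (W - B)/B.

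- A reduction of 50% or more means W ≤ 0.5B, which gives R ≤ -50%.
- The cut-off as read, R ≤ 50%, means W ≤ 1.5B.
- If R had been defined as percent reduction, 100 × (B - W)/B, the rule would be R ≥ 50%.

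Neither sign convention yields R ≤ 50%.

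**Step 2: highest Week 12 count accepted, for whole-day counts.**

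| Baseline MMDs | R ≤ 50% as read | R ≤ -50% |
|---|---|---|
| 4 | 6 | 2 |
| 8 | 12 | 4 |
| 14 | 21 | 7 |

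For example, 8 to 12 days gives R = +50 and is a response as read, while 8 to 13 gives R = +62.5 and is not. Under the intended rule 8 to 4 (R = -50) is a response and 8 to 5 (R = -37.5) is not.

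**Step 3: all possible outcomes.** Baselines 4 to 14 and Week 12 values 0 to 28 give 11 × 29 = 319 pairs.

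- As read, the rule accepts the sum of floor(1.5B) + 1 over the baselines: 146 + 11 = 157 pairs.
- The intended rule accepts the sum of floor(0.5B) + 1: 47 + 11 = 58 pairs.
- Of the 99 extra pairs, 41 are improvements of less than 50%, 11 are unchanged and 47 are worse than baseline.

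These are counts of possible outcomes, not of participants.

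**Step 4: the SAP's own bands.** SAP 8.8.1 uses "High Frequency Episodic Migraine (HFEM; 8-14 MMDs) or Low Frequency Episodic Migraine (LFEM; 4-7 MMDs" at run-in. A participant going from 6 to 8 or 9 days, or from 7 to 8, 9 or 10, moves up from the low to the high band and still counts as a responder as read. From a baseline of 10 the cut-off is 15 or more, above the top of the high band.

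**Step 5: headache days.** SAP 6.2 notes: "Baseline MMDs is a subset of baseline MHDs". Baseline MHDs can therefore exceed 14. Since 1.5 × 18 = 27 and 1.5 × 19 = 28.5, at a baseline of 19 or more every Week 12 value up to 28 is accepted and the outcome no longer matters.

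**Step 6: effect on the arm comparison.** Let q be the share of an arm with -50% < R ≤ 50%. Then:

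difference as read = intended difference + (q for CT-132 - q for control).

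The sign of the last term is not fixed by the documents. To illustrate, assume a baseline of 8 for everyone, normal changes with SD 5.8, and CT-132 lower by 1.6. The 5.8 and 1.6 are the SAP 4.2 planning values; the rest is assumed.

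- Control mean change -2. As read: Φ(6/5.8) = 85.0% and Φ(7.6/5.8) = 90.5%, a difference of 5.5 points. Intended: Φ(-2/5.8) = 36.5% and Φ(-0.4/5.8) = 47.3%, a difference of 10.7 points (from unrounded values).
- Control mean change +2. As read: Φ(2/5.8) = 63.5% and Φ(3.6/5.8) = 73.3%, a difference of 9.8 points. Intended: Φ(-6/5.8) = 15.0% and Φ(-4.4/5.8) = 22.4%, a difference of 7.4 points.

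The error can therefore shrink or enlarge the difference. These figures show direction only and are not estimates of the trial's effect.

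**The case against.** The strongest objection is that there may be no error in the SAP. The finding rests on one character in a formula converted from PDF. That conversion broke the hypothesis notation in SAP 8.1.2 and dropped hyphens elsewhere, for instance in the term run-in in SAP 3.2. This possibility stands. Against it, minus signs survive in SAP 6.1 (study days), in 8.2.2 (the -7 threshold) and in the definition of R itself. A lost sign is possible but not shown.

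Second, the words settle the intent: the criterion sentence, the section heading, SAP 3.2 and the protocol all require at least a 50% reduction. That is correct, and it means harm arises only if the symbol is coded literally. It does not make the symbol right.

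Third, the stakes are small. SAP 8.6 makes secondary p-values and intervals nominal, and the MHD version is exploratory. This also stands, and it limits the weight of the point.

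Fourth, analysed MMDs may not be whole days, because the rule is applied to imputed datasets and the imputation detail is not in the available text; imputed baselines might also fall outside 4 to 14. That qualifies the pair counts in Steps 2 and 3. It leaves the contrast between 1.5 and 0.5 times baseline unchanged.

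**Conclusion.** The point holds for the text as read. The inequality contradicts both the words beside it and the SAP's own definition of R, under either sign convention, and no available passage corrects it. Appendix A, to which SAP section 8 sends the MMD derivation, is not in the available text, so whether it contains responder coding is unknown.

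The threshold is out by a full baseline count: 1.5 times baseline is accepted where 0.5 times was meant. The reach is the 50% MMD responder endpoint in the ITT and mITT sets, and the exploratory MHD responder endpoint. The primary analysis, the success criterion and the sample size are unaffected. This should be fixed but does not threaten the trial's main conclusion. Confidence is medium, because the conclusion assumes that the source PDF also lacks the minus sign. If the sign is there, the point falls away.

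**What to change.** 1. Check the criterion in the source PDF of SAP 8.5.1 for a minus sign.
2. If it is absent, change the criterion to R ≤ -50%. Equivalently, redefine R as (Baseline - Week 12)/Baseline × 100 and require R ≥ 50%.
3. SAP 8.7.13 then follows by reference. Confirm that any responder coding in Appendix A, and the analysis programs, use the same rule.

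Make the change before database lock and unblinding, so that the responder definition is not chosen after results are known. The cost is a one-character correction to the SAP, with no operational consequence.
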